10.8 Cancer-Related Pain

The improvement in cancer-related pain will be summarized using the proportion of days using analgesic to the total number of days during treatment in the study. The WHO Drug anatomical therapeutic class and generic name that represent analgesic drugs will be used to identify the use of analgesic therapy after the study treatment is administered.

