27. All concomitant medication will be documented in the CRF if taken within 28 days prior to Study Day 1, and either (whichever occurs sooner): a) 28 days after last dose of study treatment or b) initiation of alternate anti-cancer therapy. In addition, all anti-cancer medications and concomitant medications required to treat CDX-011-related SAEs taken throughout the duration of study follow-up should also be recorded.
28. For patients who develop grade 3 rash possibly related to CDX-011 and who provide appropriate consent, punch biopsies and photographs of the rash site, as well as uninvolved skin, are strongly encouraged. Samples may be submitted for central analyses including quantification of GPNMB expression; in these cases, collection, processing and shipping instructions will be provided separately.
29. Adverse event monitoring on Cycle 1 Day 7 and Cycle 1 Day 14 can be performed in person or by telephone to determine if the patient is experiencing any adverse events.
30. Events occurring > 28 days after discontinuation of study treatment are only reportable if serious (SAE) and potentially treatment-related.

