3.3 Exploratory Endpoints

- Quality of life as measured by EORTC-QLQ-C30 and/or cancer-related pain as reflected by reduced analgesic use

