10.7 Health-Related Quality of Life (HRQOL)

HRQOL will be assessed in a subset of patients using the EORTC quality of life core questionnaire-30 (QLQ-C30, version 3). The EORTC QLQ-C30 consists of 30 individual items, each representing single- or multi-item scales. Of the 30 questions, 24 aggregate into 9 multi-item scales representing the following HRQOL dimensions: 5 functioning scales (physical, role, emotional, cognitive, and social), 3 symptoms scales (fatigue, nausea and vomiting, and pain), and 1 global measure of health status ([Table 4](#)). The remaining 6 single-item scales assess the following symptoms: dyspnea, insomnia, appetite loss, constipation, diarrhea, and the perceived financial impact of the disease treatment.

The individual items on both EORTC questionnaires will be scaled and scored according to the EORTC QLQ-C30 Scoring Manual ([Fayers 2001](#)). The raw scores will be transformed to a linear scale ranging from 0 to 100, where higher scale scores indicate better HRQOL for the global health status and functioning scales, and worse HRQOL for the symptom scales. Differences from baseline of at least 10 points will be classified as the minimum clinically meaningful change in an HRQOL measure ([Osoba 1998](#); [Maringwa 2011](#)). Changes of more than 20 points will be classified as large effects. For example, an increase of 10 points on a functional scale will represent a moderate improvement, whereas a decrease of 10 points will represent moderate worsening. Changes of less than 10 points will be regarded as no change, or as clinically irrelevant.

The functional scales will be scored as follows:

$$Score = \left\{ 1 - \frac{(RS - 1)}{range} \right\} \times 100$$

where *range* is the difference between the possible maximum and minimum response to individual items. Where the majority of items take values from 1 to 4, giving *range* = 3.

Raw score (RS) is the mean of the component items:

$$RS = (I_1 + I_2 + I_3 + \dots + I_n) / n$$

Similarly, the symptom scales/items and global health status will be scored as follows:

$$Score = \{(RS - 1) / range\} \times 100$$

For multi-item scales, if at least half the items in the scale are complete, then the scale score will be calculated based on the items for which data are available. Otherwise, the scale score will be set to missing. Under this approach, none of the single-item measures will be imputed.

Table 4: Scoring the EORTC QLQ-C30 (version 3.0)

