The initial HRQOL analysis will evaluate the EORTC QLQ-C30 scores (global health status and each individual function/symptom scale) longitudinally using a linear mixed effects model for repeated measures. This model, which assumes missing data are MAR, will describe the rate of change in HRQOL scores over time for each treatment arm, taking into account the between-patient variability by incorporating each patient's individual starting point and individual rate of change. The MIXED procedure in SAS will be used with patients as the random effect; treatment arm will be defined as the fixed effect. The model also will include linear time effects (i.e., week) and time by treatment interaction terms. A covariance structure that follows an autoregressive (AR) process dependent only on the prior HRQOL assessment will be used (i.e., AR-1). If there is model convergence issue, then compound symmetry covariance structure will be used.

Because missing HRQOL data are anticipated to be related to worsening prognosis, a sensitivity analysis will be performed using a pattern-mixture model to assist in the analysis of potentially non-ignorable missing data. For this analysis, patients will be stratified into groups based on their treatment arm and timing of study dropout for HRQOL assessment (anticipated to be largely due to disease progression and death). Patients will be classified as “dropouts” if their last HRQOL assessment was prior to 6 months and as “completers” if their last assessment was 6 months or later. Mixed effects models will be created within each stratum, which will provide for separate estimates of treatment effect for “dropouts” and “completers”. Parameter estimates for each stratum will then be combined into a weighted average for the entire treatment arm. As noted previously, selected demographics and disease characteristics also will be summarized for “dropouts” and “completers” separately to evaluate if the missing HRQOL data are MAR.

A check of the distributional assumptions for the longitudinal models will be performed, along with diagnostics to examine residuals and the presence of any outlying and influential observations. The results from the data checking and model diagnostics will be presented in a separate report.

The HRQOL objective is considered exploratory. For all HRQOL scales, the p-values will be evaluated in an exploratory manner using a nominal significance level of 0.05 (2-sided).

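### SAP 10.8 registers fewer days of analgesic use but not a step to a weaker or stronger drug class, so for patients on daily analgesia it cannot tell step-down from opioid escalation

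*SAP*

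**What the plan says.** The exploratory objective (Protocol section 6, SAP section 2) and the exploratory endpoint (SAP 3.3) concern quality of life and/or "cancer-related pain as reflected by reduced analgesic use". Neither document says whether reduced use means fewer days, a lower dose or a weaker drug.

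SAP 10.8 gives the only working definition: "the proportion of days using analgesic to the total number of days during treatment in the study". On identifying analgesics it says: "The WHO Drug anatomical therapeutic class and generic name that represent analgesic drugs will be used". This applies to medication taken once study treatment has been given. Class and generic name thus decide whether a medication counts as an analgesic. They do not enter the score, and 10.8 has no term for class, strength or dose.

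Three other provisions bear on the point:

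- **Pre-treatment medication.** Footnote 27 to the schedule in SAP 1.2 says: "All concomitant medication will be documented in the CRF if taken within 28 days prior to Study Day 1". Section 10.8 makes no use of this record.
- **Medication summaries.** SAP 9 codes all medications to the WHO Drug Dictionary, lists them individually, and summarizes them by arm, therapeutic class and generic name.
- **Pain scale.** SAP 10.7 scores the QLQ-C30 pain scale (items 9 and 19) and fits a longitudinal mixed model to "global health status and each individual function/symptom scale".

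**The concern.** A yes/no count per day has a ceiling. For a patient who needs some analgesic every day throughout treatment, the score is fixed at 1.0. The change of most interest in that patient may be a move between opioid and non-opioid treatment, and the score is the same in either direction.

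An analgesic endpoint is useful beside a pain score because a pain score can improve when analgesia is intensified. The medication measure should help separate relief with less analgesia from relief with more. In patients on continuous analgesia, the measure in 10.8 cannot do this.

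**Working it through.** The documents state no figure for this endpoint, so there is nothing to reproduce. The check applies the definition to constructed patterns.

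**Inputs.** The definition comes from SAP 10.8 and the 21-day cycle from SAP 7.4 and 11. Four cycles, 4 × 21 = 84 treatment days, is an assumption for illustration, as is a change at day 21. The score is days with any analgesic ÷ 84. The last column is opioid days ÷ 84, which 10.8 does not report.

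| Pattern over 84 days | Any-analgesic days | Score under 10.8 | Opioid-day proportion |
|---|---|---|---|
| A. Opioid daily throughout | 84 | 84/84 = 1.00 | 84/84 = 1.00 |
| B. Opioid daily for 21 days, then non-opioid daily for 63 | 84 | 84/84 = 1.00 | 21/84 = 0.25 |
| C. Non-opioid daily for 21 days, then opioid daily for 63 | 84 | 84/84 = 1.00 | 63/84 = 0.75 |
| D. Non-opioid daily throughout | 84 | 84/84 = 1.00 | 0/84 = 0.00 |
| E. Any analgesic daily for 21 days, then none | 21 | 21/84 = 0.25 | depends on drug |
| F. Any analgesic daily for 21 days, then alternate days (32 of 63) | 53 | 53/84 = 0.63 | depends on drug |
| G. None for 63 days, then any analgesic daily for 21 | 21 | 21/84 = 0.25 | depends on drug |
| H. Never | 0 | 0/84 = 0.00 | 0/84 = 0.00 |

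**Class.** A to D all score 1.00. B is a step down and C an escalation, and 10.8 gives them the same value. The opioid-day proportion separates them, 0.25 against 0.75.

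**Dose.** The same holds within one drug. Take daily use at 100 arbitrary units, with any change after day 21:

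- constant: mean daily dose 100
- halved: (21 × 100 + 63 × 50)/84 = 62.5
- cut by 90%: (21 × 100 + 63 × 10)/84 = 32.5
- doubled: (21 × 100 + 63 × 200)/84 = 175

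All four score 1.00.

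**Days.** E, F and H show the other side. Stopping, or using analgesics on fewer days, lowers the score to 0.25, 0.63 or 0.00.

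**Baseline.** E and G share the score 0.25 although use fell in one and rose in the other, because 10.8 has no baseline value and no change over time. That gap is separate, and closing it would not by itself solve the class problem. A patient on daily analgesia before treatment who follows B or C goes from 1.00 to 1.00, a change of 0 on the any-analgesic scale.

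**The case against.** The strongest reply is that fewer days on analgesics is an ordinary meaning of reduced use, and 10.8 measures exactly that. This stands. A reader might infer that the measure cannot register reduced analgesic use at all, or cannot move for anyone who starts as a daily user. Patterns E and F refute both: only a patient who remains on daily analgesia throughout is held at 1.0.

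A reader might also want to state a percentage by which the treatment effect is diluted, equal to the share of daily users. The documents do not support this. They give no such share. Staying on daily analgesia is itself an outcome after randomization, so treating those patients as a fixed, uninformative fraction conditions on the result. If one arm has fewer of them, the score shows it.

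The second reply is that the information appears elsewhere. This stands in part. SAP 9 reports medication by class and arm, but its text plans no days of use and no direction of change. The QLQ-C30 pain scale measures pain directly, but it does not measure analgesic use. It also covers only patients fluent in a language in which the questionnaire is validated, and the primary analysis needs a completed baseline questionnaire.

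The third reply is that little depends on this, and that is correct. The objective is exploratory and worded as and/or, 10.8 plans no test, and the multiplicity procedure in SAP 10.1 covers PFS, ORR and OS only. The table shells are in a separate document (SAP 16) that was not available, so a breakdown by class there cannot be ruled out.

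**Conclusion.** The point holds in a limited form. As written, 10.8 responds to the number of days with analgesia and not to drug class or dose. For patients on daily analgesia throughout treatment, a step-down and an escalation to opioids give the same value, 1.0. This follows from the definition alone and needs no assumption about the data; the 84-day patterns only illustrate it.

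The effect on the comparison between arms cannot be quantified from the documents, because neither the share of such patients nor the frequency of class changes is given. The importance is low, since the endpoint is exploratory and descriptive. It is still worth correcting, because a better answer to the trial's own question is available from data already collected.

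**What to change.** In SAP 10.8, keep the any-analgesic-day proportion and add, by arm:

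- (a) the proportion of treatment days with an opioid;
- (b) the shift in highest analgesic class (none, non-opioid, opioid) from the 28-day pre-treatment window to the treatment period.

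Derive both from the WHO Drug class and generic name already coded, and present them beside the QLQ-C30 pain scale from 10.7.

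Two details should be written down. First, (a) and (b) need to be read together. Highest class over the whole treatment period shows an escalation. It shows a step-down from an opioid only if the patient takes no opioid on any treatment day. A later step-down, as in pattern B, appears only in (a). Second, the pre-treatment window needs one anchor. The schedule footnote counts back from Study Day 1, whereas Protocol section 9 counts back from randomization, which may precede first treatment by up to 5 days.

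The cost is SAP wording and a little more programming, with no new data collection. Dose changes within a class, and a switch from a stronger to a weaker opioid, would still go unmeasured, and the text should say so.

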All concomitant medication will be documented in the CRF if taken within 28 days prior to randomization, and either (whichever occurs sooner): a) 28 days after last dose of study treatment (either CDX-011 or capecitabine chemotherapy), or b) initiation of alternate anti-cancer therapy. All anti-cancer medications taken throughout the duration of study follow-up (including the initiation of anti-cancer medications representing the reason for discontinuation of treatment or study) should also be recorded, as should concomitant medications required to treat CDX-011-related SAEs.

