24. Imaging-based evaluation per RECIST 1.1 should be performed in accordance with the Site Manual provided by Celldex (or designee). Contrast-enhanced CT of the chest, abdomen, and pelvis, as well as all other suspected disease sites is required. MRI exams of the brain, abdomen, and pelvis can be performed in lieu of a CT; however MRI exams of the chest are not recommended. In the event that a chest MRI is performed, a non-contrast chest CT is strongly recommended to evaluate the lung parenchyma. Brain and/or bone scans are required for any patients with a history of metastases to bone and/or brain or where symptomatology raises the suspicion for bone and/or brain metastases. Lesions identified on bone scans should be confirmed by a CT or MRI at baseline, and, if identified as target lesions due to soft tissue component, they should continue to be followed by the same methodology (i.e., CT or MRI scan). However, bone lesions followed as non-target disease may be subsequently followed by bone scans only. Lesions that cannot be imaged but are assessable by clinical exam may be assessed using color photography including a ruler (preferred method) or measured with calipers. Normally, all target and non-target disease sites should be evaluated at each assessment. However, for patients with non-target bone disease, bone scans need only be repeated every twelve weeks. The same method of assessment and the same technique should be used to

characterize each identified and reported lesion at baseline and during follow-up. Target lesions selected for tumor measurements should be those where surgical resection or radiation are not indicated or anticipated.

25. Randomization may be performed up to 5 days prior to initiation of study treatment, but should occur only after confirming all eligibility criteria have been met.
26. Unless otherwise specified, all study assessments should be performed prior to administration of study treatment, and may be performed up to 24 hours prior to treatment administration if assessments remain within the specified visit window.

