2 STUDY OBJECTIVES

Primary Objective

- To evaluate the anti-cancer activity of CDX-011 in metastatic, GPNMB over-expressing, triple-negative breast cancer as measured by the duration of progression-free survival (PFS).

Secondary Objectives

- To further assess the anti-cancer activity of CDX-011 in metastatic, GPNMB over-expressing, triple-negative breast cancer, as assessed by the objective response rate (ORR), duration of response (DOR), and overall survival (OS).
- To further characterize the safety of CDX-011 in metastatic, GPNMB over-expressing, triple-negative breast cancer.
- To obtain pharmacokinetic parameters and to explore the relationship between patient-specific measures of exposure and safety and activity parameters.

Exploratory Objective

- To assess whether treatment with CDX-011 is associated with improvement in quality of life and/or cancer-related pain as reflected by reduced analgesic use.

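### SAP 10.8 reports an on-treatment level of analgesic use as improvement, with no pre-treatment baseline, so it cannot show a reduction within a patient or arm

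*SAP*

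**What the plan says.** - **Objective and endpoint.** SAP section 2 sets an exploratory objective of "improvement in quality of life and/or cancer-related pain as reflected by reduced analgesic use". SAP section 3.3 lists the endpoint as "cancer-related pain as reflected by reduced analgesic use". Protocol section 6 has the same objective.
- **Planned statistic.** SAP section 10.8 states that improvement will be summarised using the "proportion of days using analgesic to the total number of days during treatment in the study". Drug dictionary codes will be used to "identify the use of analgesic therapy after the study treatment is administered". The section gives no pre-treatment proportion, change score, covariate, responder definition or between-arm test.
- **Medication records.** SAP Table 1, footnote 27 (and the same footnote in the protocol) says: "All concomitant medication will be documented in the CRF if taken within 28 days prior to Study Day 1". Protocol section 9 anchors the window differently: "All concomitant medication will be documented in the CRF if taken within 28 days prior to randomization". Footnote 25 links the two anchors: "Randomization may be performed up to 5 days prior to initiation of study treatment".
- **Nearby rules.** SAP section 7.6 defines baseline as the value closest to, but not after, first dose. SAP section 9 tabulates prior and concomitant medications by therapeutic class and generic name.

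**The concern.** Improvement and reduction are statements about change, and the planned statistic contains nothing to measure change from. A report that follows section 10.8 to the letter could describe a low on-treatment proportion as improved pain in patients who needed few analgesics to begin with. It could equally miss a real fall in patients who entered on daily analgesics and still needed them on some days.

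The rest of the SAP does not work this way. QLQ-C30 scores are judged by difference from baseline (section 10.7), and laboratory values and vital signs are summarised with change from baseline (sections 12.3 and 12.5). The analgesic measure lacks a starting point even though the protocol already requires medication from the four weeks before treatment to be recorded.

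What is at stake is limited: whether one exploratory summary answers its own objective.

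**Working it through.** The documents give no rate, standard deviation, power or sample-size figure for analgesic use, so there is no stated figure to reproduce. The check is whether the statistic can register a reduction, and then what a baseline would add.

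**1. Can the statistic register a reduction?** Planned statistic: P = analgesic days on treatment / days on treatment. Change from baseline: P − B, where B = analgesic days in the 28 days before Study Day 1 / 28.

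Daily use throughout treatment gives P = 1.0. With B = 28/28 the change is 0; with B = 0/28 it is +1.0. The planned statistic is 1.0 in both cases.

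Illustration with assumed values, 42 analgesic days out of 84 on treatment (P = 42/84 = 0.50):

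| Pre-treatment days | B | P | P − B |
|---|---|---|---|
| 28/28 | 1.00 | 0.50 | −0.50 |
| 14/28 | 0.50 | 0.50 | 0.00 |
| 7/28 | 0.25 | 0.50 | +0.25 |
| 0/28 | 0.00 | 0.50 | +0.50 |

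A fall, no change and a rise all give 0.50.

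**2. Does another section supply B?** No. The rule in SAP section 7.6 picks a single last value, which is not a proportion of days. The tabulation in SAP section 9 shows which drugs were used, not for how many days.

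**3. Are the records there?** Under footnote 27 the window is exactly the 28 days before Study Day 1. Under protocol section 9 it starts 28 days before randomization, and randomization is at most 5 days before first dose, so it opens up to 28 + 5 = 33 days before Study Day 1. Either way the 28 days before Study Day 1 are covered. The documents do not say that medication start and stop dates are captured. That is an assumption, but counting analgesic days on treatment needs them too.

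**4. How large could a chance imbalance be?** With the planned 200 and 100 patients, the standard error of a between-arm difference in mean baseline is SD × √(1/200 + 1/100) = 0.12 SD. The 95% chance limits are ±1.96 × 0.1225 = ±0.24 SD. At an assumed correlation ρ of 0.5 to 0.7 with equal SDs, an imbalance at that limit carries 0.24 × 0.5 = 0.12 SD to 0.24 × 0.7 = 0.17 SD into an unadjusted comparison.

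**5. What would a baseline do for precision?** Variance relative to the unadjusted on-treatment comparison, assuming linearity and equal variances before and on treatment:

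| Assumed ρ | Covariate adjustment, 1 − ρ² | Change score, 2(1 − ρ) |
|---|---|---|
| 0.5 | 0.75 (25% removed) | 1.00 (no gain) |
| 0.7 | 0.51 (49% removed) | 0.60 (40% removed) |

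The covariate is therefore the better use of the baseline in a comparison; the change score is for description. Neither column comes from the documents. A proportion of days is bounded and may pile up at 0 and 1, so these factors are rough.

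**The case against.** **Randomization makes a baseline unnecessary.** The objective asks whether CDX-011 is associated with improvement, and lower on-treatment use than in the control arm would be evidence of that. This stands in part. A reader might infer that the endpoint can say nothing about treatment; that goes too far, because leaving out the baseline does not bias a between-arm contrast. But section 10.8 plans no such contrast, and what it says it summarises is improvement.

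**The harm is to a comparison nobody has planned.** Correct: section 10.8 is descriptive, with no test or model. Imbalance and precision matter only if the arms are compared, formally or by eye. The mismatch between label and statistic does not depend on that.

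**Pain already has a baseline-anchored analysis.** Correct. The QLQ-C30 pain scale (items 9 and 19) has a baseline, a 10-point threshold for meaningful change and a longitudinal model in SAP section 10.7, and the objective is worded and/or. It covers only a subset of patients, limited by language, and it measures reported pain rather than analgesic use. It softens the gap without filling it.

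**Prior medication will be visible by arm.** SAP section 9 will show which analgesics were used, but not days of use. The table shells are in a separate document that is not available here and may say more.

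**The statistic does separate some patients.** A reader might suppose that someone on daily analgesics throughout and someone who begins them at progression would score alike. They would not: treatment stops at progression, so the late starter scores near 0 and the daily user near 1. The failure concerns patients with equal on-treatment use and different earlier use.

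**Conclusion.** The point holds, at minor severity. SAP section 10.8 labels an on-treatment level as improvement, and that level takes the same value whether use fell, stayed the same or rose from before treatment. It cannot show a reduction within a patient or arm, which is what the objective and endpoint name.

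No gain can be quantified from the documents. One might be tempted to turn the correlation range into a saving in patients. The documents do not support that: they give no correlation, no test is powered or planned here, and the larger gains belong to covariate adjustment rather than to a change score. The conclusion about the label rests on the wording alone; the feasibility of the remedy rests on medication dates being captured. The primary PFS analysis and the controlled secondary tests are untouched.

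**What to change.** In SAP section 10.8:

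1. Define the baseline as the proportion of analgesic days in the 28 days before Study Day 1, using the drug codes already chosen for the on-treatment count. State Study Day 1 as the single anchor, since protocol section 9 uses randomization.
2. Summarise the baseline proportion, the on-treatment proportion and the change by arm.
3. State that any between-arm comparison will use the baseline proportion as covariate (ANCOVA, or rank ANCOVA given the bounded scale).
4. Confirm that medication start and stop dates are on the CRF.

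If the dates turn out not to support this, the minimum is to rename the quantity as on-treatment analgesic use and not call it improvement.

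The cost is SAP wording and one derived variable. If the dates are captured, there is no new data collection and no burden on patients.
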